## PROMIS WOMAN Education Program : ImProving ceRvical cancer preventOn methods among Muslim Americans WOMEN

### Conflict of Interest

The PI should ask the questions on this page of all research personnel who are engaged in the research, including subrecipient investigators and personnel.

1. \* To the best of your knowledge, do you (as PI) or any other engaged individual have a financial interest related to this study?

*Financial interest include utilizing your licensed intellectual property in the study; serving as a paid consultant, or advisory board member, or officer/director with a related entity; and equity or business ownership in a company that is related to this project*

Yes  No

2. \* To the best of your knowledge, do you (as PI) or any other engaged individual have a non-financial interest related to this study?

*Non-financial Interests could include such things as:*

- utilizing your unlicensed intellectual property in the study,
- serving as an unpaid advisory board member or officer/director with a related entity, and
- equity or business ownership in a company that has yet to make a profit and is related to this project
- conflict of time/effort,
- personal and professional relationships/affiliations,
- intellectual passions or personal beliefs
- other factors that could create bias in the study

Yes  No

3. Describe any institutional conflict of interest that you or any member of the research team are aware of that pertains to this research:

An institutional conflict of interest is a situation in which financial interests of the University or University leadership may affect research activities at VCU.

## PROMIS WOMAN Education Program : ImProving ceRvical cancer preventOn methods among Muslim Americans WOMEN

### Other VCU Requirements

This page asks questions on behalf of other ancillary offices, committees and departments at VCU regarding institutional requirements that could apply to this research. In some cases, these requirements could also impact the consent process or other aspects of the IRB's review.

Based upon answers provided earlier in this form, certain ancillary sections below may not have questions displayed if those requirements are not applicable to this study.

#### 1. Cost Coverage Analysis

**Information on coverage analysis requirements and processes can be found through VCU's Clinical Research Compliance Program at <https://research.vcu.edu/human-research/clinical-research/vcu-clinical-research-coverage-analysis/>**

1. \* VCU requires that all clinical research studies be evaluated to determine if a Coverage Analysis is required. Has your study been evaluated by an institutionally designated Coverage Analysis Specialist?

Yes

No

Not Applicable

#### 2. ClinicalTrials.gov Program & OnCore

For guidance, see <https://cctr.vcu.edu/support/consultation/clinical-trials-gov/> or email [[contact]](mailto:[contact])

1. \* Is this a Clinical Trial?

Yes  No

2. \* The PI acknowledges awareness of the following requirements for posting clinical trial consent forms:

- Each clinical trial under the 2018 Common Rule that is conducted or supported by a Federal department or agency must post one IRB-approved consent form that was used to enroll subjects on a publicly available Federal website [45 CFR 46.116(h)].
- When engaged in multi-site research, the VCU PI is responsible for confirming with the lead site who is responsible for posting the informed consent form.
- When VCU is the lead site, the VCU PI is responsible for posting the informed consent form (unless

the federal department or agency will post it).

Yes  No

### 3. Community Engagement

For more information, see <https://community.vcu.edu/>

1. \* Is this a community engaged research study? (See help text for definitions)

Yes

No

2. \* Provide details about each community co-researcher. If there are more than 5 community partners/co-researchers, add the 5 most significant partners/co-researchers.

Organization	Zip Code / Country	Role
Islamic center of Richmond	23060	Provides access to study subjects or project sites only. Partner/Co-researcher is not involved with study design, subject recruitment, data collection, or data analysis

### 4. Family Educational Rights and Privacy Act (FERPA) Requirements

For guidance, see <https://far.vcu.edu/records/family-education-rights-and-privacy-act/>

1. \* Does this study involve obtaining information from VCU students' educational records (see help text)?

Yes

No

### 5. Research Data Privacy Requirements

Contact the **VCU Research Data Privacy Office** with questions: <https://research.vcu.edu/integrity-and-compliance/compliance/research-data-privacy/>

1. \* Does this study involve the VCU site (regardless of the IRB of record), or any sites under the VCU IRB's oversight, obtaining data in, or from, a foreign country?

Yes  No

## 6. Information Security

**For guidance, see** <https://ts.vcu.edu/askit/essential-computing/information-security/>

1. \* Using the VCU Data Classification Tool, please determine the appropriate data classification category for the data that will be collected or used in this research.

Note: if the data falls into Category 1, a data security management plan is required by University Information Security Office.

See help text for information on accessing the VCU Data Classification Tool, and for information on creating a data security management plan at <https://dms.vcu.edu>.

Category 1: all data that require breach notifications in the event of improper release, including personally identifiable information covered by HIPAA and Commonwealth of Virginia regulations.

Category 2: all proprietary data that if improperly released has the potential to cause harm to the institution, its mission or its reputation that do not require breach notifications.

2. \* I confirm use of the VCU Data Classification Tool at <https://go.vcu.edu/dataclassification> in determining the data classification category selected in Question 1:

Yes

No

3. \* The PI is aware that if the study's data is classified as Category 1, a Data Management Plan must be submitted to and approved by VCU Information Security prior to IRB approval. See <https://ts.vcu.edu/askit/essential-computing/information-security/data-management-system/>

Yes  No

4. \* I confirm that any use of external technology has been submitted to Information Security in the study's Data Management Plan. If this study uses any technology platforms, apps, services, etc. that are maintained external to VCU or hosted by another institution and are NOT currently listed in the DMS system as an approved service for the storage, processing, or transmission of VCU data, I am required to have VCU Information Security conduct a security review of that technology. I may contact [[contact]](mailto:[contact]) with questions.

I also confirm that if the study involves use of external technology and VCUHS HIPAA data, I must also seek security review from the VCUHS Data Governance group (contact [name] at [[contact]](mailto:[contact])):

Yes

No

N/A - not using external technology

**7. Massey Cancer Center Protocol Review and Monitoring Committee (PRMC)**  
**For guidance, see** [https://www.masseycancercenter.org/research/-/link.aspx?\\_id=ee49e95faa8b44d09b6e89d8e3b48b57&\\_z=z](https://www.masseycancercenter.org/research/-/link.aspx?_id=ee49e95faa8b44d09b6e89d8e3b48b57&_z=z)

## 1. \* Does this study involve any of the following?

- Research involving patients with cancer, their families or their health care providers
- Research involving cancer screening, diagnosis or prevention
- Secondary data collected from cancer patients or their medical records
- Cancer-related surveys (e.g., attitudes about risk, prevention and treatment) of the general population

 Yes No

If Yes, upload documentation of PRMC approval or review.

**8. VCU ONETRAC Protocol Review Oversight Committees (PROCs) For guidance, see** <https://onetrac.vcu.edu/>

## 1. \* Does this study involve research with any of the following?

- VCU Health System patients

- VCU Health System facilities

- VCU Health System data

 Yes No**9. VCU Health Department of Patient Centered Services**

## 1. \* Does your study involve a satisfaction survey administered to VCUHS patients (\*See Help Text):

 Yes No Not Applicable**10. VCU Faculty-Held IND or IDE**For guidance, see <https://research.vcu.edu/human-research/regulatory-affairs/>.Questions related to if you need an IND or IDE for your study should be emailed to: [[contact]](mailto:[contact]). Please submit a

copy of your FDA submission prior to submitting to the FDA to <https://redcap.vcu.edu/surveys/?s=NR7K7LR4JW>.

## 11. VCU Health System locations

1. \* Will research activities occur in patient care areas of the VCU Health System (including at CHoR, Community Memorial Hospital, Tappahannock Hospital, VCU Medical Center and Massey Cancer Center)?

Yes  
 No

## 12. VCUHS Department of Pathology

**Learn more about requesting and establishing an account with Pathology here: See**

<https://pathology.vcu.edu/research-services/>

1. \* I have contacted VCUHS Department of Pathology to determine feasibility if my study involves the following:

- Storage of Microbiology isolates
- New instrumentation provided by clinical trial/study sponsor, or
- Non-routine specimen processing (examples include but aren't limited to the following: addition of reagents to samples/aliquots, buffy coat processing, DNA sample processing)

Yes  
 No  
 N/A - my study does not involve any of the listed processes.

2. \* If my study involves specimen retrieval from the Pathology laboratory, I have established a process with Pathology to deidentify and retrieve specimens.

Yes  
 No  
 N/A - my study won't involve specimen retrieval from Pathology

## 13. VCU Institutional Biosafety Committee (IBC)

**To contact the Biosafety Office see their website at:** <https://research.vcu.edu/integrity-and-compliance/compliance/regulatory-committees/>

1. \* Does this project involve any of the following hazardous biological agents ("biohazardous agents") that have NOT been FDA approved? These may include, but are not limited to, any of the following. If you are unsure, please contact the Biosafety Office:

- Any functional recombinant viruses (especially viruses that may integrate into the patients' genome).

- Expression or administration of biological toxins.

- Live pathogenic or potentially pathogenic organisms of plants or animals (bacteria, fungi, wild-type viruses, parasites, etc.), that are, or potentially may be, in experimental products.

- Introduction or expression of rDNA or synthetic nucleic acids

- Use of a product (e.g., monoclonal antibodies, recombinant cytokines) produced from virally infected mammalian cells.

- Use of a product (purified growth factors, cytokines) produced from mammals or their cells.

Yes  No

**14. VCU Radiation Safety Committee (RSC)**

**To contact the Radiation Safety Section see their website at:** <https://research.vcu.edu/integrity-and-compliance/compliance/regulatory-committees/>

1. \* Does this study involve radiation exposure and/or scans involving radiation (e.g.: PET, MRA, CT, DXA, nuclear medicine, etc.)?

Yes

No

**15. VCU Scientific Review Committee (SRC)**

**For guidance, see** <https://ccctr.vcu.edu/support/consultation/scientific-review-committee/>

1. \* Has this human subjects protocol (not the grant application) already been reviewed by the funder of a sponsored project (e.g. a federal, state or non-profit funding sponsor)?

Yes

No

View	[name] Resume	[name] 06.07.2021.pdf	0.01	4/3/2022 3:47 PM	[name]	CV/Biosketch	Not Applicable

## **PROMIS WOMAN Education Program : ImProving ceRvical cancer preventOn methods among Muslim Americans WOMEN**

### **Institutional Requirements Complete**

Protocol Progress:

- INITIAL SETUP
- BACKGROUND, RATIONALE & GOALS
- RESEARCH PLAN
- CONSENT PLAN
- RISKS, PRIVACY & CONFIDENTIALITY
- POPULATIONS WITH SPECIAL CONSIDERATIONS
- INSTITUTIONAL REQUIREMENTS
- ⑧ DOCUMENTS

Click Continue below to go to the next section

## PROMIS WOMAN Education Program : ImProving ceRvical cancer preventOn methods among Muslim Americans WOMEN

### Documents

1. Upload any documents that the VCU IRB will need to conduct a review of this submission:  
A list of potential documents is given in the help text.

**NOTE: The delete function should only be used if an incorrect document is uploaded or added to the system AND that document has not been reviewed and approved by the IRB. Do NOT delete documents that the IRB previously reviewed and approved.**

Once you have uploaded a document to RAMS-IRB, any changes to that document (i.e. different versions of the same document) should be added to the IRB submission by using the Update button. To provide updated documents, follow these steps:

- Click the Update button located to the left of the document to be updated.
- In the Add Document window, click the Choose File or Browse button, select the file you are adding, and click on the Open button.
- Click OK to close the Add Document window, and the system will upload the revised document. RAMS-IRB will automatically provide a version number for the document.

To access previous versions of a document in RAMS-IRB you must use the History link associated with the document.

- Click the View or Update button located to the left of the document you wish to access.
- In the Add/View Document window, click the "History" hyperlink located to the right of the file name.
- A separate window will open that shows all versions of the document that have been added to RAMS-IRB. Click on any file name to download and view the document.

Document Name	Document	Version	Date Modified	Uploaded Type	Approved
View Consent form focus group	[name]- Consent from of focus group	0.03	7/8/2023 1:09 AM	[name]	Consent/Assent/Information Sheet
View Consent form - Intervention program	[name]- Consent from of Intervention group	0.04	7/8/2023 1:09 AM	[name]	Consent/Assent/Information Sheet
View Fund Plan	[name] -Budget 04.13.2023.xlsx	0.03	5/12/2023 11:52 AM	[name]	Funding Proposal
					Not Applicable

Document Name	Document	Version	Date Modified By	Uploaded Type	Approved
---------------	----------	---------	------------------	---------------	----------

View Education session	[name] Education session guide , intervention group-04.07.2023.docx	0.02	5/12/2023 10:52 AM	[name] Other	Yes
View Timeline Plan	[name], timeline for PROMIS women Project-.docx	0.02	5/12/2023 10:43 AM	[name] Other	Yes
View Conceptual model	[name] Conceptual Model 05.12.2023.docx	0.02	5/12/2023 10:40 AM	[name] Research Measure	Yes
View Flayer 2	[name] Flyer Version 05.12.2023.docx	0.01	5/12/2023 10:39 AM	[name] Other	Yes
View [name]-Focus group script guide	[name] -Focus Group Script Guide.docx	0.02	5/12/2023 10:24 AM	[name] Other	Yes
View Participants -RA communication script	Participants -RA communication script .docx	0.01	5/12/2023 6:45 AM	[name] Other	Yes
View Study Survey( Pre-post and satisfactory scales)	Survey- Promise women project 05.12.2023.docx	0.01	5/12/2023 6:35 AM	[name] Research Measure	Yes
View consent form- focus group	Consent from - Focus group 02.20.2023.docx	0.01	2/20/2023 4:32 PM	[name] Consent/Assent/Information No Sheet	
View VS biosketch	[name] Biosketch for AN 11.14.2022.pdf	0.01	2/20/2023 4:00 PM	[name] CV/Biosketch	Not Applicable
View Communication log	Communication log.docx	0.01	2/20/2023 3:59 PM	[name] Other	Yes
View PRMC approval	2022-10-10 MCC-22-19873_PRMC Approval Letter.pdf	0.01	10/10/2022 12:30 PM	[name] Ancillary Committee Approval	Not Applicable

Document Name	Document	Version	Date Modified By	Uploaded Type	Approved
View Flyer	Flyer 004.08.2022.png	0.01	4/8/2022 6:09 PM	[name]	Other
View [name] Resume	[name] 06.07.2021.pdf	0.01	4/3/2022 3:47 PM	[name]	CV/Biosketch

ID: HM20024502

HM20024502

HM20024502 - [name]

## **PROMIS WOMAN Education Program : ImProving ceRvical cancer preventOn methods among Muslim Americans WOMEN**

### **Documents Complete**

Protocol Progress:

- INITIAL SETUP
- BACKGROUND, RATIONALE & GOALS
- RESEARCH PLAN
- CONSENT PLAN
- RISKS, PRIVACY & CONFIDENTIALITY
- POPULATIONS WITH SPECIAL CONSIDERATIONS
- INSTITUTIONAL REQUIREMENTS
- DOCUMENTS

End of Application

Click Continue below to exit and submit this project

# Consent Groups

**1. \* Enter a descriptive name for this consent / assent group:**

Focus group consent form

**2. \* Select all that apply to this consent / assent group:**

Name
 Signed Consent by Participant
 Signed Parent/Guardian Permission or Legally Authorized Representative Consent
 Signed Assent by Child or Decisionally Impaired Adult
 Verbal/Other Indication of Assent by Child or Decisionally Impaired Adult
 Short Form Consent (limited applicability)
 None of the Above (select waiver below)

**3. \* Select all electronic signature platforms that apply to this consent / assent group:**

 Not using electronic signature platforms
 DocuSign Part 11 (FDA regulated studies)
 DocuSign (standard platform for non-FDA regulated studies)
 REDCap e-Consent
 iMedConsent (Veterans Affairs studies)
 Other electronic signature platform

**4. If Other is selected, explain:****5. \* Select any waivers that apply to this consent / assent group:**

No Waivers Requested	
 Waiver of All Consent or Some Elements in Consent Form	
 Waiver of Parental Permission or Legally Authorized Representative Consent	
 Waiver of All Assent by Child or Decisionally Impaired Adult	
 Waiver of Signature on Consent/Permission Forms (waiver of documentation of consent)	
 Exception from Informed Consent (for emergency research only)	
6. * Select all study team role(s) that will obtain consent / assent from this group:	
Principal Investigator	
Co/Sub-Investigator	
 Medical or Psychological Responsible Investigator	
Lead Student/Trainee Investigator (leading their own project)	
Research Coordinator	
 Research Nurse	
 Consultant	

Research Assistant	
	Pharmacist
	Statistician
	Regulatory Coordinator
	Trainee/Student(working on project)
	Other
	N/A: Requesting Waiver of Consent

**7. \* Describe the consent procedures used for this group. Address each point below:**

- When and where consent will occur
- What will be covered during the consent discussion
- How the consent discussion will occur (e.g. in-person, phone, video conference)
- How you will reconfirm consent on an ongoing basis, if applicable

-The consenting process for the study will commence after receiving IRB approval, expected in May 2023, at the Islamic Center in a private room provided by the Community Advisory Board. During the consent discussion, participants will be provided with a background about cervical cancer among Muslim women. Depending on their enrollment, either in the focus group or the education session, the details of the respective components will be explained.

-The consent discussion will take place in-person, allowing for face-to-face interaction. The research assistant (RA) will provide the participant with the necessary materials and information to make an informed decision about participation. The discussion will cover the potential risks, benefits, and compensation associated with the study.

-Participants will be given the opportunity to consider their participation and make an informed decision. They will be offered the option to provide consent electronically using either DocuSign. The electronic consent form will be accessible via a provided link, ensuring convenience and ease of use for the participants.

-Ongoing reconfirmation of consent is not applicable in this study.

**8. \* Select the processes for minimizing any potential perception of undue influence to participate, particularly when there is a pre-existing relationship between the participant and the researcher (e.g. treatment**

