H1. Participants will show significant improvements in knowledge and acceptance of cervical cancer prevention after the intervention. To test this hypothesis, we will conduct a pre-post survey to examine changes in knowledge and acceptance of cervical cancer screening and prevention. This aim includes the Phase III (Efficacy) of the ORBITT model. Aim 3. We will test the feasibility and acceptability of the religiously tailored and culturally appropriate intervention program which includes education and experiential practice/communication skills training. We will recruit 20 participants with the same eligibility criteria as in Aim 1, who have not participated in our previous studies, and conduct a single-arm pilot trial. H2. We hypothesize that the religiously tailored and culturally appropriate intervention program will be feasible to conduct as evidenced by meeting enrollment targets and the ability to implement the program as planned. H3. The intervention will be acceptable as evidenced by engagement (>60%) and retention (>80%), and satisfaction survey ratings.

For these aims, we will use a survey that includes:

Pre-test survey, the scales are:

1. Demographic
2. Perceived Discrimination
3. Religious Discrimination
4. Spiritual Health Locus of Control
5. Modesty
6. Cervical Cancer Knowledge
7. Perceived risk
8. Cuse of action
9. Self-efficacy
10. Attitude about CC screening
11. HPV vaccination acceptability

Post-test survey, the scales are:

2. Perceived Discrimination
3. Religious Discrimination
4. Spiritual Health Locus of Control
5. Modesty
6. Cervical Cancer Knowledge
7. Perceived risk
8. Cuse of action
9. Attitude about CC screening
10. HPV vaccination acceptability
11. General Self-Efficacy Scale (GSES)
12. Cervical Cancer Screening Self-Efficacy Scale

Satisfactory survey are:

- Experience with the intervention.
- Acceptability of content
- Acceptability of delivery

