**See the help text for additional guidance**

**1. A statement explaining the study design**

**Study Design:**

The proposed study consists of two parts.

Part 1 involves formative research through a focus group to gather insights and reach saturation.

Part 2 is a single-arm pre and post-test trial with the objective of evaluating the efficacy of an educational interventional program.

The study aims to increase cervical cancer screening (CC-S) and HPV vaccine (HPV-Vax) rates among Muslim American women (MAW) in Virginia, leading to a reduction in cervical cancer (CC) incidence and mortality.

2. A detailed description of all the procedures that will be followed to carry out the study, preferably in sequential order, and in sufficient detail that the study's methods could be replicated.
  - a. Part 1 - Formative Research: Conduct a focus group with 10 participants until saturation is reached.
  - b. Part 2 - Single-arm Pre and Post-test Trial: Enroll 20 participants to evaluate the educational program's effectiveness.

Participants will complete a baseline survey to assess their knowledge, attitudes, CC-S and HPV-Vax practices, and predisposing factors.

The survey will cover topics such as CC knowledge, experiences of medical mistrust, discrimination, spiritual coping, and fatalism.

3. The schedule and frequency of when and how procedures will be conducted (e.g. in person, online, phone, paper, etc.)

All procedures will be conducted in person at the Islamic Centers, except for follow-up phone calls.

Recruitment will occur during regular Friday prayers and religious holidays.

Participants will receive a brochure explaining the study and be screened for eligibility by the Research Assistant (RA). Eligible participants will be given a telephone contact for enrollment at a more convenient time.

The consent process will involve verbal explanation, providing the consent form in English, and allowing participants to ask questions. Follow-up surveys and confirmations will be conducted via phone calls.

4. A description of all research measures/tests/interventions that will be used, including analyses/tests conducted on specimens/biological samples (if applicable)

**Power Analysis:** No power analysis for this study. A target sample size of 20 participants has been determined based on PhD committee, the purpose of the project is training for the STUDENT.

Measures: Validated scales and surveys will be used to measure

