**When and Where Consent Will Occur:**

Consent for the intervention group will be obtained at the Islamic Center during the scheduled education sessions. Participants will have the opportunity to provide consent before engaging in the educational program.

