**What Will Be Covered During the Consent Discussion:**

During the consent discussion, participants will be provided with a detailed explanation of the educational program, including the topics covered, session duration, and expected outcomes. The risks and benefits associated with participation will be clearly explained, along with any potential discomfort or adverse effects that may arise from the educational sessions. Additionally, participants will be informed about their rights as research participants, including confidentiality and the voluntary nature of their involvement. They will have the opportunity to ask questions and seek clarifications before providing consent.

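### Consent for the education trial may give disease background and expected outcomes before the baseline survey, so the pre-test may be partly pre-exposed

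*Combined protocol and SAP*

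**What the plan says.** The Combined protocol and SAP describes consent in two forms, both summarised in the Consent Process table.

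- **Focus group consent form, item 7:** "During the consent discussion, participants will be provided with a background about cervical cancer among Muslim women". The next sentence reads: "Depending on their enrollment, either in the focus group or the education session, the details of the respective components will be explained". So the text sits in the Part 1 form, but its wording reaches women joining Part 2.
- **Intervention group consent form, item 7:** the discussion gives a "detailed explanation of the educational program, including the topics covered, session duration, and expected outcomes", as well as risks and benefits. It does not list disease background. On timing it says "Consent for the intervention group will be obtained at the Islamic Center during the scheduled education sessions" and "Participants will have the opportunity to provide consent before engaging in the educational program". Item 10 of the same form allows one to two weeks to decide.
- **Study Procedures, item 6:** Part 2 is a single-arm pre-post trial of 20 women. "Participants will complete a baseline survey to assess their knowledge, attitudes, CC-S and HPV-Vax practices, and predisposing factors".
- **Study Procedures, item 2 (H1):** "Participants will show significant improvements in knowledge and acceptance of cervical cancer prevention after the intervention".
- **Study Procedures, item 4:** the month 0 (baseline) survey is given after the educational material has been delivered.

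**The concern.** H1 rests on the change from baseline within one group. A control group that had the same consent discussion would carry the same exposure, and the comparison would cancel it. Here nothing does. The baseline therefore has to measure women before they meet the programme's content.

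Two parts of the consent discussion could work against that. Disease background bears on the pre-test scales for cervical cancer knowledge and perceived risk, and cervical cancer risk is one of the three session topics. Hearing the expected outcomes shows women which answers the team hopes for on attitude and acceptability items. Both are avoidable features of the consent script, and a pre-test cannot be repeated once the session has been given.

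**Working it through.** No figure in the plan bears on this point, so there is none to reproduce. The check has three steps.

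**1. Order of events**

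- Consent comes before the programme (Intervention group consent form, item 7).
- Consent is signed, with no waiver (items 2 and 5), and the study is done exclusively for research (Study Procedures, item 7). A baseline survey would therefore normally follow consent. This is an inference; no section states it.
- Consent is taken at the scheduled sessions, yet women have one to two weeks to decide. The discussion could come minutes or days before the baseline survey.
- Study Procedures, item 4, puts the baseline survey after the education material, which conflicts with the pre-post design in items 1 and 6.
- Behavioral Intervention/Task Details gives a 3-hour event with a 90-minute session and a 45-minute survey. That leaves 180 − 90 − 45 = 45 minutes for break and lunch. A second 45-minute survey at the event would leave 180 − 90 − 90 = 0. The schedule does not show where the pre-test fits.

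**2. Overlap with what is scored**

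- The content and depth of the background are not described, and the survey and consent forms are separate uploads. Overlap with particular items cannot be shown.
- One possible route is visible. Both consent forms cover benefits. The direct-benefits answer (Background, Rationale and Goals, item 5) includes women coming to know that the HPV vaccine is safe and effective. An example survey item in Study Procedures, item 6, asks whether the respondent believes exactly that. If staff described benefits in those terms, they would state the favoured answer. Nothing in the plan prevents it.

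**3. Scale, by illustration only**

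Let d be the true standardised knowledge change and f the share of it already present at baseline because of the consent discussion. The measured change is d × (1 − f). Power of a paired t-test with n = 20 uses the noncentral t distribution with 19 degrees of freedom and noncentrality d(1 − f)√20, two-sided 0.05. The plan gives no values for d, f, alpha or sidedness; all are assumed.

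| d | f = 0 | f = 0.10 | f = 0.25 | f = 0.50 |
|---|---|---|---|---|
| 0.5 | 56.5% | 48.0% | 35.7% | 18.6% |
| 0.8 | 92.4% | 86.3% | 72.1% | 39.7% |
| 1.0 | 98.9% | 96.8% | 88.9% | 56.5% |

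A small f costs little; a large one would matter. The documents do not say which applies.

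**The case against.** The strongest reply is that the disease background appears only in the focus group form, that Part 2 has its own form without it, and that a background could mean no more than the study's rationale: disparities and late diagnosis. The investigators' own survey of 100 women found that most already knew of cervical cancer; the gaps were HPV and the Pap test, which the background is not said to cover. Some disclosure before baseline is unavoidable in any consented study. For knowledge the bias is conservative. The trial is also a 20-woman pilot without a power analysis.

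Much of this stands, and it rules out several stronger readings that a reader might infer:

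- *Every Part 2 woman is taught programme content before baseline.* The text supports only that background is provided, by wording that extends to Part 2. Its depth is not given.
- *The baseline no longer measures unexposed knowledge and attitudes.* The order is inferred and the effect may be small.
- *Two biases run in opposite directions and cannot be corrected.* Hearing expected outcomes could colour baseline answers, post-survey answers or both, so its net direction is unknown.
- *Satisfaction ratings are contaminated at baseline.* Satisfaction has no baseline measurement.
- *A stated percentage of the gain is lost.* Any such figure only restates the share assumed.

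The reply does not remove the point. The sentence that follows the background text names the education session, and the Part 2 form independently includes expected outcomes. The investigators' earlier interviews also found minimal information about HPV, vaccination and screening, so a low baseline could move with little input.

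**Conclusion.** The point holds in a limited form. As written, the consent procedures may expose Part 2 women to disease background, and do expose them to expected outcomes, before the programme begins and probably before the pre-test. With no control group, any learning at consent would be subtracted from the measured knowledge gain. Cueing could move attitude and acceptability changes either way.

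The size is unknown and could be close to zero. The conclusion rests on two assumptions: that consent precedes the baseline survey, and that the focus group wording is applied to Part 2 as it reads.

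It ranks below the conflict over when the baseline survey is given. If Study Procedures, item 4, were followed literally, the whole 90-minute session would precede the baseline and the consent discussion would add little. Correcting that conflict alone would still leave the pre-test after the consent discussion, so this wording needs its own small correction. It is a cheap improvement, not a fatal flaw.

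**What to change.** 1. For Part 2, state one order: consent, baseline survey, education session, post survey. Reconcile Study Procedures, item 4, with items 1 and 6, and show where each survey falls in the event schedule.
2. In item 7 of both consent forms, and in the matching Consent Process table, limit the Part 2 discussion to purpose, procedures, topic headings, risks, benefits, payment and rights. Word it neutrally, free of content scored in the survey.
3. For Part 2, give the cervical cancer background only after the baseline survey has been handed in.
4. Replace the mention of expected outcomes with a description of what the surveys will ask about.

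The cost is one IRB wording amendment. Women lose no information that consent requires, and the background still reaches them later. The change does not remove all exposure: the statement of purpose and benefits, the flyers and brochure, and the Imam's introduction all still come before the baseline.
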